7.1 EXTENT OF EXPOSURE

Not applicable.

7.2 ADVERSE EVENTS

AEs are recorded throughout the study and at early termination. They are coded using the MedDRA coding dictionary (the database will document the version current at the time of data lock).

7.2.1 Treatment-emergent Adverse Events

A treatment-emergent adverse event (TEAE) is defined as any event occurring after the first ISWT in the study or any event already present that worsens in either intensity or frequency.

Only TEAEs will be summarized. Any AE starting prior to the first ISWT in the study will be excluded from the summary analyses.

The following subsections note the planned presentations of TEAEs. Other presentations for TEAEs may be produced to support the Sponsor's review and analyses of events of special interest.

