6 STATISTICAL METHODS

6.1 DATASETS FOR ANALYSES

This study has the following analysis populations:

- All Subjects (All): Subjects who consented to the study protocol.
- Full Analysis Set (FAS) Population: Subjects who enrolled in the study protocol (initiated Day 1 procedures). Tabulations for endpoint analyses will be conducted on this population.
- Per-Protocol (PPROT) Population: Subjects who completed the study protocol, do not have significant protocol deviations in the study, and were appropriately included to investigate the research hypotheses. The Sponsor will assess inclusion of this population at the time of database lock. Endpoint analyses may be conducted from this population if the population is applicable after Sponsor review.
- Safety Population: Subjects who initiated the ISWT at Screening.
- Psychometric Analysis Population (PAP): Subjects who completed the PGI-S items or Modified Borg Scale at any visit or time point.

Summary tables will be presented with the number and percentages of subjects overall and by cohort.

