7.2.2 Date of Onset of Adverse Event

The onset date of each AE will be the date recorded on the eCRF.

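### SAP 7.2.1 both includes and excludes an AE that starts before the Screening walk and later worsens, and does not place an AE that starts during that walk

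*SAP*

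**What the plan says.** SAP 7.2.1 defines a TEAE as "any event occurring after the first ISWT in the study or any event already present that worsens in either intensity or frequency". It continues: "Only TEAEs will be summarized". It then adds: "Any AE starting prior to the first ISWT in the study will be excluded from the summary analyses".

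Other provisions bear on how this rule works:

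- SAP 6.1 defines the Safety Population as "Subjects who initiated the ISWT at Screening", so the first ISWT in the study is the Screening walk.
- SAP 7.2.2 states: "The onset date of each AE will be the date recorded on the eCRF". Protocol 9.2 has onset times, as well as dates, entered in the eCRF.
- Protocol 9.2 starts AE collection at informed consent, and the schedule in Protocol 3.2 marks AE assessment in the Screening ISWT column itself.
- Protocol 7.1 asks for Screening to be done in one day where feasible.
- Protocol 9.1.1 allows worsening of existing symptoms or conditions caused by study procedures to be recorded as an AE. Appendix 15.4 asks for the maximum intensity of an AE.
- In SAP section 11, all five AE tables (14.3.1.1 to 14.3.1.5) are TEAE tables. The two AE listings named are deaths (14.3.2.1) and SAEs (14.3.2.2).

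**The concern.** The three sentences of SAP 7.2.1 should sort every AE as in or out of the tables, and they do not. One class of event receives two opposite answers. Another receives no clear answer and is lost on a literal reading. Two programmers could produce different AE tables from the same data.

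Both classes matter for this study. No drug is given, and the walk is the procedure that the study imposes. The test is described to subjects as maximal, chest pain is a listed reason for stopping, and the Screening result caps the later walks. A subject who starts the Screening walk but completes fewer than 3 shuttles fails eligibility, yet belongs to the Safety Population with that walk as the only exposure. Safety is a stated objective, and procedure-related events are what it should describe.

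**Working it through.** No figure in the plan underlies this point, so the check is one of logic. Each combination of onset and later course is taken through the three sentences of SAP 7.2.1.

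| Case | Onset relative to Screening ISWT | Worsens later? | TEAE definition | Exclusion sentence | Result |
|---|---|---|---|---|---|
| 1 | Before | No | Not met | Excludes | Out, consistent |
| 2 | Before | Yes | Met, second limb | Excludes | Contradiction |
| 3 | During | No | Not met if *after* means after the walk ends | Silent | Left out on a literal reading |
| 4 | During | Yes | Depends on when *already present* is judged | Silent | Undetermined |
| 5 | After | No | Met | Silent | In, consistent |
| 6 | After | Yes | Met | Silent | In, consistent |

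Three of the six cases are settled (1, 5, 6), one is contradictory (2), one is omitted on a literal reading (3) and one is undetermined (4).

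**Can case 2 occur?** Yes. AEs are collected from consent, which precedes the walk. Appendix 15.4 points to one record per AE at its maximum intensity, and neither document tells sites to open a new record when an AE worsens. The original onset would then stand, and the exclusion sentence would apply. The second limb also gives no reference time for the worsening.

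**Can case 3 occur?** Yes. AEs are assessed during the walk. The two anchors in the SAP differ: the population is fixed by initiating the walk, while the TEAE definition runs from after it.

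**Where would such an event appear?** Not in Tables 14.3.1.1 to 14.3.1.5, if the restriction to TEAEs is applied literally. A death or SAE would still be in Listings 14.3.2.1 and 14.3.2.2, whose titles carry no treatment-emergent limit. For a non-serious event, SAP section 11 names no AE output. Table 14.2.2.6 would show chest pain as a reason for ending the walk, but not as an AE. Protocol 10.3.3 planned an AE summary without a TEAE restriction, but SAP section 1 says that the SAP supersedes the protocol's statistical considerations.

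**Reach.** Case 2 needs onset between consent and the Screening walk, a short window if Screening is done in one day. Cases 3 and 4 need onset within the Screening walk, which is 1 of 3 planned walks. Screening recovery, the interval to Day 1, and both Day 1 walks with their recoveries all come after the first ISWT and are captured.

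**The case against.** The strongest reply is that the intent is clear enough. *After* the first ISWT can be read as after it begins, as the Safety Population wording suggests, and the exclusion sentence does not remove an event that starts during the walk. That is a fair reading, but the SAP does not state it, and it leaves the contradiction over worsened AEs untouched.

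Several stronger readings are tempting and are not supported:

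- *Every safety summary is affected.* Only the five AE tables are. Deaths, SAEs and vital signs have their own outputs, and disposition reports reasons for discontinuation.
- *A non-serious event would be reported nowhere.* SAP section 11 is headed as a list of tables and figures, and Protocol 10.3 and 10.6 still promise data listings. The absence of an all-AE listing from a list that does name two others is suggestive, not proof.
- *Every pre-existing condition that worsens is lost.* Under Protocol 9.1.1 a medical-history condition made worse by the walk can be entered as a new AE with later onset, and would be kept.
- *One third of exercise-related events are lost.* One walk in three is not one third of the AE risk. AEs are collected over as much as 15 days, and only the minutes of one walk are in doubt.
- *TEAE status is decided by date alone.* SAP 7.2.2 says where the onset date comes from. It does not forbid use of the onset time. This is missing detail, although with one-day Screening the date alone could not order an event against the walk.

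It is also fair to say that this is a descriptive study of about 40 subjects, with no study drug and no inferential safety testing.

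**Conclusion.** The point holds within these limits. SAP 7.2.1 contradicts itself for an AE that starts between consent and the Screening ISWT and later worsens. Read literally, it also leaves an AE that starts during that walk outside the TEAE definition. Non-serious AEs of these kinds can be missing from all five AE tables. The number cannot be estimated from the documents and is probably small.

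The conclusion assumes that the sentences are applied as written and that sites keep one AE record, with its original onset, when an AE worsens. If sites open a new record on worsening, the contradiction reaches fewer events, but the wording is still inconsistent. Because the stated rule gives a wrong or undefined answer for events that the study itself may cause, it should be corrected rather than left to the programmer.

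**What to change.** Replace the rule in SAP 7.2.1 with one that has a single anchor:

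- A TEAE is an AE with onset at or after the start of the Screening ISWT, or an AE present before that time that worsens in intensity or frequency afterwards.
- Only AEs that started before the Screening ISWT and did not worsen afterwards are excluded from the summaries.
- Classification uses the onset date and time in the eCRF. An AE dated on the day of the Screening ISWT with no time recorded counts as treatment-emergent. This last rule is a convention that errs toward inclusion.

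Two additions would complete it: a sentence on how worsening is recorded or identified, given that Appendix 15.4 asks for maximum intensity, and a listing of all AEs in SAP section 11.

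The core change is SAP wording, because Protocol 9.2 already collects onset times. The downside is that a few more events may be counted, some of them with onset shortly before the walk when the time is missing. The listing is one more output.

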7.2.2 Date of Onset of Adverse Event

The onset date of each AE will be the date recorded on the eCRF.

7.2.3 Intensity Rating

The Investigator classifies AEs into 1 of the following intensity categories: "Mild," "Moderate," and "Severe."

7.2.4 Relationship to Study Drug

Not applicable.

7.2.5 Action Taken with Study Drug

Not applicable.

7.2.6 *Outcome*

For each AE, the investigator denotes the outcome of the AE under one of the following: “Fatal,” “Not recovered/Not resolved,” “Recovered/Resolved,” “Recovered/Resolved with Sequelae,” “Recovering/Resolving,” or “Unknown.”

7.2.7 *Caused Study Discontinuation*

The investigator denotes if the AE caused study discontinuation (“Yes,” “No”).

7.2.8 *Summary of Treatment-emergent Adverse Events*

TEAEs will be summarized overall and by cohort for the following:

- Total number of TEAEs, total number subjects with at least 1 TEAE
- Total number of serious TEAEs, total number subjects with at least 1 serious TEAE
- TEAEs by severity
- TEAEs leading to study discontinuation

TEAEs will be presented in alphabetical order of SOC and by decreasing order of incidence of the preferred terms.

For these summaries, a subject having the same TEAE multiple times will only be counted once for the corresponding preferred term. Similarly, a subject who experienced multiple TEAEs within the same SOC will be counted only once for that SOC.

A subject experiencing the same TEAE multiple times or at multiple severities will only be counted once under that preferred term at the worst severity rating. Similarly, a subject who experiences the same TEAE multiple times or at multiple severities across multiple preferred terms within the same SOC will only be counted once for the worst severity rating within the SOC.

7.2.9 *Subgroup Analysis*

TEAEs may be summarized within subgroups if suggested by the data.

7.3 VITAL SIGNS

Descriptive statistics for vital signs (SBP, DBP) will be presented by study visit, overall, and by cohort as raw data, and by change from Baseline within study visit.

7.4 INTERIM ANALYSES

This is an observational study and data may be evaluated at any time during the study.

8 PATIENT GLOBAL IMPRESSION OF SEVERITY QUESTIONS

[REDACTED] [REDACTED] [REDACTED]

[REDACTED]

[REDACTED] [REDACTED]

[REDACTED] [REDACTED]

[REDACTED] [REDACTED]

[REDACTED] [REDACTED]

[REDACTED] [REDACTED]

[REDACTED] [REDACTED] [REDACTED]

[REDACTED] [REDACTED]

[REDACTED] [REDACTED]

[REDACTED] [REDACTED]

[REDACTED] [REDACTED]

[REDACTED] [REDACTED]

[REDACTED] [REDACTED] [REDACTED]

[REDACTED] [REDACTED]

[REDACTED] [REDACTED]

[REDACTED] [REDACTED]

[REDACTED] [REDACTED]

[REDACTED] [REDACTED]

9 MODIFIED BORG DYSPNEA SCALE

The person administering the test will obtain a rating of dyspnea using the Borg dyspnea scale.

The person will use the following dialogue:

“I would like to use the following scale to indicate your shortness of breath at this moment (indicate the Borg dyspnea scale). If there is no shortness of breath at all you will point to 0; if the shortness of breath is not very great you will choose from 0.5 to 2; if you are somewhat more short of breath you will select 3; and if the breathing is getting very difficult, you will choose 4 to 9, depending on just how hard it is; 10 represents the greatest shortness of breath you have ever experienced in your life. If one of the numbers does not exactly represent how short of breath you are at this moment, then you can choose a fraction in between. For example, if you have shortness of breath somewhere between 4 and 5, you can choose 4.5.”

Perceived Breathlessness (Borg Scale)

- 0 NOTHING AT ALL
- 0.5 VERY VERY SLIGHT (just noticeable)
- 1 VERY SLIGHT
- 2 SLIGHT
- 3 MODERATE
- 4 SOMEWHAT SEVERE
- 5 SEVERE
- 6
- 7 VERY SEVERE
- 8
- 9 VERY VERY SEVERE (almost maximum)
- 10 MAXIMUM

11 LIST OF TABLES AND FIGURES

Table No.	Title	Population
14.1.1	Summary of Subject Accountability and Disposition	All
14.1.2	Summary of Analysis Populations	All
14.1.3	Summary of Demographic and Baseline Characteristics	All
14.1.4	Summary of Medical and Surgical History	All
14.1.5.1	Summary of Prior Medications	All
14.1.5.2	Summary of Concomitant Medications	All
14.1.6	Summary of Protocol Deviations	All
14.2.1.1	Summary of PGI-S Change from Baseline	All
14.2.1.2	Summary of PGI-S Change from Baseline	PPROT
14.2.1.3	Figures for PGI-S Change from Baseline	FAS
14.2.1.4	Figures for PGI-S Change from Baseline	PPROT
14.2.1.5	Summary of PGI-S Time to Recovery	FAS
14.2.1.6	Summary of PGI-S Time to Recovery	PPROT
14.2.2.1	Summary of Borg Change from Baseline	All
14.2.2.2	Summary of Borg Change from Baseline	PPROT
14.2.2.3	Summary of Pulse Oximetry and Heart Rate	All
14.2.2.4	Summary of Pulse Oximetry and Heart Rate	PPROT
14.2.2.5	Figures for Pulse Oximetry and Heart Rate	FAS
14.2.2.6	Summary of ISWT	All
14.2.3.1	PGI-S Response Frequency (%) Distributions	PAP
14.2.3.2	PGI-S Construct Validity Correlations	PAP
14.2.3.3	PGI-S Known-Groups ANOVAs	PAP
14.2.3.4	PGI-S Test-retest Reliability	PAP
14.2.3.5	PGI-S Responsiveness	PAP
14.3.1.1	Summary of Treatment-emergent Adverse Events by System Organ Class and Preferred Term in Decreasing Order	Safety
14.3.1.2	Summary of Treatment-emergent Adverse Events by Preferred Term in Decreasing Order	Safety
14.3.1.3	Summary of Serious Treatment-emergent Adverse Events by System Organ Class and Preferred Term in Decreasing Order	Safety
14.3.1.4	Summary of Treatment-emergent Adverse Events by Severity by System Organ Class and Preferred Term in Decreasing Order	Safety
14.3.1.5	Summary of Treatment-emergent Adverse Events Leading to Study Discontinuation by System Organ Class and Preferred Term in Decreasing Order	Safety

14.3.2.1	Listing of Deaths	Safety
14.3.2.2	Listing of Serious Adverse Events	Safety
14.3.3	Summary of Vital Signs	Safety
